Hypothesis: The WBF and FPS-R will demonstrate convergent validity when used to measure acute pain in children presenting to the emergency department

Rationale: Both the WBF and FPS-R have been studied for their use in obtaining self-reports of pain in children, and overall have been determined to be two of the preferred methods of pain assessment in pediatric patients. Although each has been compared to other methods of pain measurement, the two have not been compared to each other. If the two studies were proven to have convergent validity, it would strengthen the evidence that these methods should be the preferred tools for assessing pain in children.

Methods Summary: Prospective, observational study to determine the convergent validity of the WBF and FPS-R for children presenting to the ED with acute pain. The initial and repeat WBF and FPS-R self-report scores will be compared in patients presenting to the ED with acute pain.

Phase 2 – Secondary Aim #2

To determine if there is inter-rater reliability between patients presenting to the pediatric ED with acute pain and their caregivers when using the WBF and FPS-R at two separate time points during their ED evaluation

Hypothesis: There will be low inter-rater reliability between patients and their caregivers using the WBF and FPS-R.

Rationale: Caregiver perception of a pediatric patient's pain is often used as a substitute for the patient's self report of pain; however, studies are limited to show that caregivers are able to predict children's pain level accurately when in the acute care setting.

Methods Summary: Prospective, observational study to determine the inter-rater reliability between patients and their caregivers when using the WBF and FPS-R. The initial and repeat WBF and FPS-R self-report scores will be compared to caregivers' initial and repeat WBF and FPS-R ratings in patients presenting to the pediatric ED with acute pain.

Identification of Subjects

Participants will come from a convenience sample of children presenting to the ED. Triage nurses and ED providers will be aware of the study and notify the PI or designee by phone if patients may qualify for the study. The PI and designees will also have access to the ED trackboard and can screen for possible participants.

Inclusion Criteria

Patients \geq 3 years and \leq 7 years six months old Chief complaint of pain or painful condition (Phase 1 only) Pain score \geq 4/10 (Phase 2 only) Caregiver speaks English or Spanish

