Exclusion criteria

Altered mental status History of traumatic brain injury (TBI) History of developmental delay History of Autism History of chronic pain, defined as persistent or recurrent pain in children with chronic health conditions⁸ Non-verbal patients

Outcome Measures:

Phase 1 - Primary Aim

Rate of intended script use in pain scale delivery Review of themes during nursing pain assessment Consistency in delivery of WBF by nursing

Phase 2 - Primary

Neurocognitive development score BRIGANCE ® score Initial WBF score Repeat WBF score Initial FPS-R score Repeat FPS-R score Anchor report of pain (a lot better, a little better, the same, a little worse, a lot worse)

Phase 2 - Secondary

Initial WBF score (patient and caregiver) Repeat WBF score (patient and caregiver) Initial FPS-R score (patient and caregiver) Repeat FPS-R score (patient and caregiver)

Study Definitions:

"Caregiver" will refer to an adult who is able to provide consent for treatment and provides regular care for the child.

"Chronic pain" includes persistent (ongoing) and recurrent (episodic) pain in children with chronic health conditions.

Convergent validity evaluates the degree to which two different scales that are supposed to measure the same thing produce similar results.

"Repeat pain score" will be completed approximately 20 minutes after the initial pain score, or if administered, approximately 20 minutes after analgesic intervention.

Responsivity is the degree to which a test behaves in a manner that is consistent with what the test is purported to measure. It determines whether the measure is able to identify changes in pain over time that are clinically important to patients.

Phase 1 Study Protocol:

- 1. Once the subject is identified, the caregiver will provide verbal consent for participation in the study.
- 2. After verbal consent is obtained, the primary investigator will observe and audio record nursing's assessment of the patient's pain and complete the observation checklist (Appendix 1).

Phase 2 Study Protocol:

- 1. Once the subject is identified, the caregiver will provide written consent for participation in the study (if a self-report pain score was not collected in the triage process, patients with pain or a potentially painful condition will have their pain assessed using an age appropriate self-report pain scale by the PI or designee).

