- 2. Early in the ED visit, the investigator or designee will help the patient complete Part One of the Patient Survey (Appendix 3), which includes the WBF, and the FPS-R.
- 3. The caregiver will also complete Part One of the Caregiver Survey (Appendix 4).
- 4. Subjects will be treated per usual care by an MD/ACP.
- 5. The investigator or designee will help the patient complete Part Two of the Patient Survey (Appendix 3), which includes the WBF and the FPS-R. This will occur approximately 20 minutes after analgesic administration, if it was ordered.
- 6. The caregiver will also complete Parts Two and Three of the Caregiver Survey (Appendix 4).
- 8. If the patient indicates that he/she feels the same or worse on Part Two of the Patient Survey the treating MD/ACP will be notified.
- 9. The patient will be reassessed by the PI or designee at least 20 minutes after analgesic administration, if it was ordered, or after a reasonable time period if no analgesic medication was ordered.
- 10. On reassessment, if the patient says that he/she is willing to participate, the PI or designee will complete a brief neurocognitive skills assessment (Appendix 2) as well as the BRIGANCE ® Early Childhood Screens III with the patient. If the patient is not willing to participate, study assessments will cease.

Statistical Analysis:

Phase 1

Sample size: 30

Rate of compliance with intended script and rate of consideration of caregiver perception will be reported as percentages. Qualitative data will also be reviewed by the PI for the emergence of themes.

Phase 2

Sample size: approximately 250

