Responsivity will be measured by correlating the change in the WBF and FPS-R scores before and after analgesic intervention with the anchor change in pain score (a lot better, a little better, the same, a little worse, a lot worse). Pearson correlations will be estimated between each change score and the anchor score. In addition, we will use ANOVA to test the difference in mean pain change among the children reporting "a lot better", "a little better", and "the same". For the scales to be considered responsive, we would need to see significant reductions for the children reporting "a lot better", minimal to no reduction for those reporting "the same", and increase in pain for those reporting "worse". We will need a relatively large number of children in each category (a lot better, a little better, the same) to be able to test for differences (at least 30 per group). We will use Fisher's z-transformation to test if level of neurocognitive development impacts responsivity. Levels of neurocognitive development will be defined as at or above expected or lower than expected. The Fisher's z-transformation formally tests if the correlations between two measures (change in pain and anchor rating) differ between two groups. Here we assume we will have significant variability in change scores and in the anchor ratings to conduct these correlations and the formal test. We would need at least 56 children in each neurogcognitive development group (expected or above versus below). If the variability is limited in that most children report improvement and few report same or worsening, we will test for responsivity differences using a two-way ANOVA where the two factors are self reported anchor response ("better", "same" or "worse) and neurocognitive level (expected or above expected vs below expected). The outcomes are the change in the WBF and the change in the FPS-R. The test of interest will be the two way interaction between the anchor and the neurocognitive development level. The BRIGANCE also provides the developmental age for each child which can be compared to their actual age. We will test if this difference is significant using a paired t-test. We will also explore the age where responsivity worsens by conducting similar analyses but stratified by actual age (each year) and developmental age. Given the proposed analysis, we will need at least 50 children for each cognitive age (3, 4, 5, 6, and 7 years) assuming at least 10 fall into the "a lot better", "a little better", "the same" categories for the anchor pain question.

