Appendix 4 – Caregiver Survey (Phase 2 Secondary Aim #2)

Part One

Thank you for agreeing to participate in this study of pain scales used in children. Your responses will help us make sure we are doing the best job we can to address your child's pain. Please do not ask your child about his/her pain while you answer these questions.

What do you believe is hurting on your child?

These faces show how much something can hurt. The face on the far-left shows no pain. The faces show more and more pain up to the far-right. It shows very much pain.

Please circle the face that shows how much you think your child hurts right now.

Each face below is for a person who has no pain, or some, or a lot of pain. Face 0 doesn't hurt at all. Face 2 hurts just a little bit. Face 4 hurts a little bit more. Face 6 hurts even more. Face 8 hurts a whole lot. Face 10 hurts as much as you can imagine, although you don't have to be crying to have this worst pain.

Please circle the face that represents your child's pain right now.

Part Two

Your child has received medications to help lessen his/her pain. Please answer the following questions about your child and his/her level of pain right now.

Please do not ask your child about his/her pain while you answer these questions.

These faces show how much something can hurt. The face on the far-left shows no pain. The faces show more and more pain up to the far-right. It shows very much pain.

Please circle the face that shows how much you think your child hurts right now.

Each face below is for a person who has no pain, or some, or a lot of pain. Face 0 doesn't hurt at all. Face 2 hurts just a little bit. Face 4 hurts a little bit more. Face 6 hurts even more. Face 8 hurts a whole lot. Face 10 hurts as much as you can imagine, although you don't have to be crying to have this worst pain.

Please circle the face that represents your child's pain right now.

Do you think your child is in less pain than when you last rated his/her pain in Part One? (Circle your answer)

Yes No

If yes, what makes you believe his/her pain is less`?

If no, what makes you think his/her pain is not less?

Part Three

If you do not feel that your child's pain has improved, please notify a provider at this time.

Please answer the following questions about your child's ability to report his/her pain.

Do you think that your child would understand the pain scales you used to rate his/her pain?

(Circle your answer)

Yes No

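### A child given an ED analgesic before Part One may have an anchor and a score change that cover different intervals: no rule requires Part One first, and the child's anchor names no reference time

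*Combined protocol and SAP*

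**What the plan says.** **Timing of the repeat score.** Study Definitions places it "approximately 20 minutes after the initial pain score, or if administered, approximately 20 minutes after analgesic intervention". Phase 2 Study Protocol, step 5, repeats the drug-based clock for Part Two: "This will occur approximately 20 minutes after analgesic administration, if it was ordered".

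**Intended order.** Step 2 reads "Early in the ED visit, the investigator or designee will help the patient complete Part One" of the survey, step 4 "Subjects will be treated per usual care by an MD/ACP", and step 5 is Part Two. In Appendix 3 the medication name and time sit between the two parts. In Appendix 4 only Part Two tells the caregiver "Your child has received medications to help lessen his/her pain". Statistical Analysis, Phase 2, measures responsivity by "correlating the change in the WBF and FPS-R scores before and after analgesic intervention" with the anchor.

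**What comes before Part One.** Identification of Subjects says "Triage nurses and ED providers will be aware of the study and notify the PI or designee by phone"; screening from the trackboard is the other route. Phase 2 step 1 then requires written consent. The exclusion list has no entry for an earlier analgesic.

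**The two change questions.** In Appendix 3, Part Two, the child is asked whether he or she feels better, worse or unchanged, then whether by a little or a lot. No earlier moment is named. In Appendix 4, Part Two, the caregiver's question names the Part One rating as its reference.

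**Use of the anchor.** It is correlated with score change for Primary Aim #1. For Primary Aim #2, accurate use means that the self-report agrees with the child's stated change in pain.

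**The concern.** The child's anchor is the yardstick for both Phase 2 primary aims, so it should cover the same stretch of time as the score change it is set against. In the intended order it very nearly does, whichever earlier moment the child has in mind.

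That protection goes if the child is dosed before the investigator reaches Part One. Phase 2 requires a pain score of at least 4/10, treatment is usual care, and Part One waits for notification and consent, so an earlier dose is plausible. Such a child may truthfully report feeling better than before the drug while the two face scores, both taken after it, barely differ. A correct answer would then look like poor scale use. Even if the child does compare with Part One, a shortened interval leaves less true change to report.

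An unstated reference time cannot be repaired after data collection, since nobody can later establish which moment the child meant.

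**Working it through.** **1. The plan's nearest figure.** The point disputes no stated number. The relevant one is 56 children per neurocognitive group for the Fisher z comparison. The plan gives no alpha, power or correlations, so 56 cannot be derived from its own inputs. Assuming two-sided 5% and 80% power, n = 2 × [(1.960 + 0.842) / (atanh r1 - atanh r2)]² + 3. For r = 0.5 against 0 this is 2 × (2.802 / 0.549)² + 3 = 55.02, rounded up to 56; 0.7 against 0.31 and 0.8 against 0.5 also give 56. The fix leaves 56 unchanged.

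**2. Interval between ratings.**
- Drug after Part One: Part Two is about 20 minutes after the drug, so at least about 20 minutes after Part One. No problem arises.
- Drug d minutes before Part One, and that dose counted as the triggering analgesic: interval = max(20 - d, 0).

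| d (min) | Part One to Part Two (min) |
|---|---|
| 5 | 15 |
| 10 | 10 |
| 15 | 5 |
| 20 | 0 |

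- Drug before Part One, and that dose not counted: the first limb of the definition applies and the interval is about 20 minutes. The anchor's reference is still open.

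**3. What each measure covers in a pre-dosed child.** The score change runs from Part One to Part Two. The anchor runs either (A) from before the drug or (B) from Part One. Under A with the earlier dose as trigger, it spans about 20 minutes against 20 - d for the scores. Under B the two coincide.

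**4. Illustration only.** None of these inputs is in the documents:
- Pre-drug pain uniform 4 to 10; relief Normal(3, 2.5), redrawn below -3 and capped at pre-drug pain; linear onset complete at 20 minutes.
- Face scores in steps of 2 with noise SD 1.5; anchor noise SD 1.5, cut at -3, -1, 1 and 4.
- 20% of children pre-dosed; 1,000,000 simulated children per scenario. A match means that the signs of score change and anchor agree.

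| | None pre-dosed | d = 10 | d = 15 | d = 20 |
|---|---|---|---|---|
| Correlation, reference A | 0.54 | 0.49 | 0.46 | 0.42 |
| Correlation, reference B | 0.54 | 0.51 | 0.52 | 0.55 |
| Match in pre-dosed children, A | 71% | 57% | 44% | 31% |
| Match in pre-dosed children, B | 71% | 51% | 39% | 35% |

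The 71% is for children dosed after Part One. A repeat run agreed to within about 0.005. If 83% of the lower group rate at random (r = 0.06), chosen so that 56 per group gives 80% power with none pre-dosed, power with 20% pre-dosed is 71-55% under A and 75-82% under B (d = 10 to 20).

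The direction is informative: under A both quantities fall; under B the correlation hardly moves but the match falls.

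**5. What the fix can and cannot do in the same model.** With relief complete at 20 minutes, retiming alone leaves reference A at 0.49-0.42; rewording the anchor moves it to 0.51-0.55. The match stays at 51-35%, because the relief has already happened. With relief complete at 40 minutes, both changes together restore the match in pre-dosed children to 51%, the value for children dosed after Part One, from 43-33% (A) or 39-34% (B).

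**The case against.** **The problem lies outside the planned sequence.** The steps, the form layout and the before-and-after wording of the analysis all put Part One ahead of the drug. This stands. What remains is a sequence the plan neither prevents nor handles, and no document says how often it occurs.

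**The 20 - d interval is one reading.** Step 5 follows treatment at step 4, so its analgesic is naturally one given after Part One. A reader might infer that the protocol requires a shortened or even zero interval. It does not; the wording is ambiguous, and an assessor would hardly repeat the scales at once. The interval holds only if the earlier dose is taken as the trigger.

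**The magnitudes are assumed.** A reader might infer from the illustration that power drops to 55%, or to 33% with 40% pre-dosed at d = 20. The documents support no such figure: share, onset, noise, match rule and both correlations are assumptions. Nor does anything suggest that early dosing differs by neurocognitive group, so a spurious group difference should not be inferred; the expected effect on that comparison is attenuation.

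**Retiming can lower the correlation.** With 30-minute onset, reference B and d = 20, the simulated correlation goes from 0.373 under the current rule to 0.340 under the new one. This does not count against retiming: rating a child twice at the same moment adds no-change pairs that lift the correlation, while the match in those children is 34%, against 42% after retiming.

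**Rewording may cue the earlier face.** Tying the anchor to the faces could prompt recall and inflate agreement with the scales under test. This is a fair cost, and it shapes the wording proposed below.

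**Conclusion.** The point holds in a limited form and merits consideration as an inexpensive improvement. Two facts are plain in the text: the treated branch of the repeat-score rule sets no minimum gap after Part One, and the child's anchor names no reference time although the caregiver's question does. They matter only for children given an ED analgesic before Part One. In those children the anchor and the score change may cover different intervals, which can weaken the correlation for Primary Aim #1 and the match for Primary Aim #2.

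The size is unknown. It depends on the share pre-dosed, how early the dose was, how fast relief comes, and which moment the child has in mind. The simulated values show direction and carry no weight as estimates. A reader might conclude that the primary analyses are invalid; the documents do not support that, because the planned order gives an adequate gap.

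**What to change.** 1. Time Part Two about 20 minutes after the later of Part One and the actual administration of the drug.
2. Word the child's anchor relative to the first rating, preferably without naming the faces, for example *than when I first asked you about your hurt*.
3. Complete Part One before any ED analgesic where this does not delay care, and record the time of any earlier dose.
4. Keep pre-dosed children in the main analysis, since responsivity is defined as "whether the measure is able to identify changes in pain over time that are clinically important to patients" and not as response to a drug. Repeat the responsivity and accuracy analyses without them as a sensitivity analysis.

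**Cost.** Two wording changes, one form field and one extra analysis; nobody leaves the main analysis. Appendix 3 already has time fields for both parts and the medication, so early doses can be identified if these are completed. Of about 250 children, the sensitivity analysis would keep 250 × 0.9 = 225, 250 × 0.8 = 200 or 250 × 0.6 = 150 if 10%, 20% or 40% are pre-dosed (assumed shares).

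**Downsides.** The question is slightly longer for young children and may still cue recall. Where the earlier dose would have set the clock, Part Two comes later: by 10 minutes at d = 10, and by 20 minutes at d = 20 or more. Items 1 and 2 cannot recover relief already complete at Part One, which is why items 3 and 4 are needed.

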
Convergent validity will be assessed by determining both Pearson's correlation and agreement using the Bland-Altman method between the WBF and FPS-R scores before and after analgesic intervention. We will compare Pearson correlations using Fisher r-to-Z transformation.

Inter-rater reliability will be determined by calculating intra-class correlation coefficients (ICCs) between the parent and the child reports at the same time points.

This analysis will be completed with the biostatistics team under the direction of CORE (Center for Outcomes of Research and Excellence).

Subject #						
Observed Pain Assessment						
Start Time:	End Time:		RN:			
Initial pain scale used						
Wong Baker FACES	Numerical	Othe	er			
Initial phrasing of question						
How is the question framed?						
Zero		Ten				
No pain		Wors	st pain exp	erienc	ed	
No hurt		Worst pain p	oossible			
Other	_	Other				
Example given for 10/10?			Yes		No	
Patient's initial response						
Time to give answer						
Is the question rephrased?			Yes		No	
Final scale used						
Wong Baker FACES	Numerical	Othe	er			
Is parent asked for confirmation?			Yes		No	
Does the parent rate the child's pa	Yes	_/10	No			
Is parent asked for their perception?					No	
Other tasks completed during assessment?					No	
Vitals Mea	lication					
Is "happy because there is no pair	Yes		No			
Is "you do not have to be crying" r	Yes		No			
Final score documented						
Does the RN believe the child und	Yes		No			
Does the caregiver believe the ch	Yes		No			

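### Beyond asking caregivers not to question the child, the plan does not keep them from hearing or seeing the child's scores, so independence of the ratings behind the child-caregiver ICC is not assured

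*Combined protocol and SAP*

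**What the plan says.** Secondary Aim #2 is "To determine if there is inter-rater reliability between patients presenting to the pediatric ED with acute pain and their caregivers", on both face scales and at two time points. The stated hypothesis is "There will be low inter-rater reliability between patients and their caregivers using the WBF and FPS-R". The rationale given is that caregiver perception often replaces self-report in practice, with limited evidence that it is accurate in acute care.

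The Phase 2 Study Protocol lists the ratings in this order:

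- Step 2, child, initial: "the investigator or designee will help the patient complete Part One of the Patient Survey (Appendix 3), which includes the WBF, and the FPS-R".
- Step 3, caregiver, initial: "The caregiver will also complete Part One of the Caregiver Survey (Appendix 4").
- Step 5, child, repeat: "The investigator or designee will help the patient complete Part Two of the Patient Survey (Appendix 3").
- Step 6, caregiver, repeat: "The caregiver will also complete Parts Two and Three of the Caregiver Survey (Appendix 4").

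Appendix 4 prints one instruction in both Part One and Part Two of the Caregiver Survey: "Please do not ask your child about his/her pain while you answer these questions".

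The Statistical Analysis section determines inter-rater reliability by "calculating intra-class correlation coefficients (ICCs) between the parent and the child reports at the same time points". It gives no ICC form, expected value or cut-off for low reliability, and says nothing about dependence between the raters.

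**The concern.** An ICC between two raters describes agreement between separate judgements only if neither rater knows the other's score. Here the child answers a member of staff, and the caregiver marks the same two rows of faces. A caregiver who has just heard the child answer, or seen the child point, can reproduce the score without asking anything, and so without breaking the Appendix 4 instruction. At the repeat, the Patient Survey opens by asking the child whether things are better, worse or unchanged, and the caregiver's Part Two then asks for new face ratings and whether pain has lessened.

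At stake is how the secondary aim is read. Scores passing from child to caregiver would push the ICC up, against the study's own hypothesis and toward endorsing caregiver ratings in place of self-report. Because exposure is not recorded, no later analysis could separate affected pairs from unaffected ones.

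**Working it through.** **Document check.** I read the Phase 2 steps, Appendices 3 and 4 and the ICC sentence together.

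- Order: the child is listed before the caregiver at both time points (2 then 3; 5 then 6).
- Separation, masking or a rule on who rates first: none found.
- Record of whether the caregiver heard or saw the child's answer: none found.
- Safeguard: the Appendix 4 instruction. It covers questioning the child while the form is filled in, and nothing else.
- Earlier exposure: Phase 2 entry needs a pain score of at least 4/10. Under step 1 a self-report score comes from triage or, failing that, from study staff. A child score may therefore be known before either survey begins.

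**No figure to reproduce.** The plan states no power, precision or target for this ICC. The Phase 2 size of about 250 matches 5 cognitive ages × 50 children = 250, which serves the analysis by cognitive age.

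**Illustration on assumed values.** Take unit variances, equal means and a true (independent) ICC ρ = 0.40. Suppose every caregiver reports (1−w) × own judgement + w × child's score. Then:

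- covariance = (1−w)ρ + w
- caregiver variance = (1−w)² + w² + 2w(1−w)ρ
- ICC = covariance ÷ [(1 + caregiver variance)/2]

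| w | covariance | caregiver variance | ICC |
|---|---|---|---|
| 0.10 | 0.36 + 0.10 = 0.46 | 0.81 + 0.01 + 0.072 = 0.892 | 0.46/0.946 = 0.486 |
| 0.25 | 0.30 + 0.25 = 0.55 | 0.5625 + 0.0625 + 0.15 = 0.775 | 0.55/0.8875 = 0.620 |
| 0.40 | 0.24 + 0.40 = 0.64 | 0.36 + 0.16 + 0.192 = 0.712 | 0.64/0.856 = 0.748 |

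Other starting values behave alike. With w = 0.25, a true ICC of 0.2 becomes 0.47 and one of 0.6 becomes 0.76.

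An alternative model has a share w of caregivers simply repeat the child's score, so that ICC = (1−w)ρ + w. With ρ = 0.40, a quarter copying gives 0.75 × 0.40 + 0.25 = 0.55, and half copying gives 0.50 × 0.40 + 0.50 = 0.70.

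**Against sampling error.** With 250 pairs, an approximate 95% interval around 0.40 is tanh(atanh 0.40 ± 1.96/√248.5) = 0.29 to 0.50. The 10% shift (0.49) falls inside it; the 25% and 40% shifts fall outside.

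**The case against.** A reader might infer that the raters are in fact not independent and that the ICC is already compromised. The documents do not support this. They do not say where the surveys are done, whether the caregiver is within hearing, or whether the child answers aloud or points. A caregiver beside a child aged 3 to 7½ years is plausible, but it is an inference.

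The sequence is also inferred. Steps 3 and 6 do not expressly place the caregiver's survey afterwards, and the ICC pairs reports from the same time points. Parallel completion fits the text. The list is not strictly chronological either, since step 9 returns to a reassessment whose timing step 5 has already covered. This weakens any statement that the caregiver always rates second. It does not remove the gap, because completing the forms side by side would leave the same opportunity to hear or see.

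The direction of bias is likely rather than certain. Appendix 4 asks whether the caregiver thinks the child understands the scales and can rate pain accurately. A doubting caregiver might disregard the child's answer or move away from it, and moving away would lower the ICC.

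The sizes are all assumed. Calling the change a move from poor to moderate agreement would import bands that the plan does not contain, and the smallest shift shown is within sampling error. Finally, the point touches a secondary aim only; the primary aims use the child's own scores and anchor report.

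**Conclusion.** The point holds as a gap in protection. The procedures do not secure the independence that the ICC needs, although the Appendix 4 instruction suggests that the authors wanted it. No contamination is shown, and its size cannot be derived from the documents.

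The consequence is asymmetric, provided that any influence draws caregivers toward the child's answer. A low observed ICC would still support the hypothesis, because the bias would have worked against it. A high ICC would be ambiguous between real agreement and shared information, and could not be taken as support for caregiver ratings as a surrogate. The figures of 0.49, 0.62 and 0.75 rest on a true ICC of 0.40, equal means and variances, and the same proportional shift in every caregiver. They show that moderate influence could outweigh sampling error at 250 pairs; they do not predict the result.

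**What to change.** - **Change the order.** At each time point the caregiver circles both faces out of the child's sight and hands in the form before staff ask the child anything. Swap steps 2 and 3. In steps 5 and 6, have the caregiver complete the Part Two ratings first.
- **Record exposure.** Add a tick box at each time point for whether the caregiver heard or saw any self-report score from the child before rating, noting which one. It must include the triage or step 1 screening score. At the repeat it should also include the child's initial study rating.
- **Add a sensitivity analysis.** Repeat the ICC without the exposed pairs and report their number beside the main result.

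The cost is a change of step order, one tick box and one further run of the planned analysis, with no extra staff or patients. The child is asked a minute or two later. Reordering cannot undo a score already heard at triage or screening; that exposure can only be recorded.

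### The search for the age at which responsivity worsens relies on separate year-by-year analyses that may have 10 children per anchor category, against the 30 the plan says a test needs, and no test compares ages.

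*Combined protocol and SAP*

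**What the plan says.** All of this stands in the Statistical Analysis section, Phase 2.

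- The total is given as "Sample size: approximately 250".
- Responsivity is measured first by Pearson correlation of each change score with the anchor rating. An ANOVA is added to compare mean change across three anchor categories (*a lot better*, *a little better*, *the same*). For that comparison the plan wants a large number of children per category "to be able to test for differences (at least 30 per group".
- To find where responsivity worsens with age, it proposes "conducting similar analyses but stratified by actual age (each year) and developmental age".
- For that work it states that "we will need at least 50 children for each cognitive age (3, 4, 5, 6, and 7 years) assuming at least 10 fall into" the three anchor categories.
- For neurocognitive level (at or above expected versus below), the plan does compare groups formally. It uses Fisher's z, or an anchor-by-level interaction in a two-way ANOVA if few children report no change or worsening. No such comparison is listed for age.

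Primary Aim #2 is to find the cognitive age equivalent from which children use the two scales accurately. Its hypothesis names five years. The age-stratified work is the only analysis in the statistical section that bears on that aim.

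**The concern.** The same kind of ANOVA is said to need 30 per category in the pooled sample, yet it is to be repeated within each age on as few as 10, with no reason given for the lower figure. The strata are then set beside one another without a test of whether responsivity differs between them.

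An age with few *same* answers could therefore look less responsive because of its counts and not because of its children. A reader could take that for a developmental threshold, which is what Primary Aim #2 sets out to locate.

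The counts are also hard to control. The anchor answer is known only at the repeat assessment. Cognitive age comes from the BRIGANCE, which is given at the end and only to children still willing (Phase 2 Study Protocol, step 10). Neither can be balanced at enrolment, and the plan itself allows that few children may report no change or worsening.

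**Working it through.** **Inputs from the plan.** Total about 250; five cognitive ages (3 to 7 years); at least 50 children per age; at least 10 per anchor category within an age (read here as 10 in each of the three categories); at least 30 per category for the pooled ANOVA.

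**Assumptions, because the plan states none.** Alpha 0.05 (two-sided for correlations); three equally spaced category means; effect size as Cohen's f, shown over a range.

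**Step 1. Reproduce the total and check that the minimums fit together.**
- 5 ages x 50 = 250, as stated.
- 5 ages x 10 = 50 per category, which satisfies at least 30.
- 3 categories x 50 = 150, which fits within 250.

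**Step 2. Per-category size within an age.** 10 / 30 = one third. Applying 30 per category within every age would take 3 x 30 x 5 = 450 children, before counting any who report worsening.

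**Step 3. Power of the ANOVA.** Place the means at -d, 0 and +d in SD units, with d² = 1.5 f². The noncentrality is the sum of n_i (m_i - weighted mean)².
- 30/30/30: 60 d² = 90 f².
- 10/10/10: 20 d² = 30 f².
- 20/20/10, with the ten at one end (*the same*): the weighted mean is -0.2 d, and 20(0.8)² + 20(0.2)² + 10(1.2)² = 12.8 + 0.8 + 14.4 = 28, so 28 d² = 42 f².

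Power from the noncentral F with 2 and N - 3 degrees of freedom:

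| f | 30/30/30 | 10/10/10 | 20/20/10 |
|---|---|---|---|
| 0.25 | 54% | 20% | 27% |
| 0.333 | 80% | 32% | 45% |
| 0.40 | 93% | 44% | 61% |
| 0.50 | 99% | 64% | 81% |
| 0.60 | >99% | 80% | 93% |

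At f = 0.333 the noncentralities are 9.97, 3.32 and 4.65. For 80% power, 10 per category needs f = 0.60.

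**Step 4. Power of the within-age correlation, n = 50.** Power is approximately Φ(atanh(r) x √47 - 1.96).
- r = 0.3: 0.310 x 6.856 = 2.12, power 56%.
- r = 0.4: 0.424 x 6.856 = 2.90, power 83%.
- r = 0.5: 0.549 x 6.856 = 3.77, power 96%.

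Power to detect a correlation at one age is not power to show that it differs from another age. With r = 0.4 and n = 50, the 95% interval on the z scale is 0.424 ± 1.96/6.856 = 0.138 to 0.710, or r from 0.14 to 0.61. Neighbouring ages would have to differ widely before their results could be told apart.

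**The case against.** A fair defence makes four points.

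1. *The two minimums do not conflict.* A reader might infer that 30 per category overall cannot supply 10 at each of five ages. The documents do not support that. Both are lower bounds for different analyses, and step 1 shows that all of them can hold together. An average of 30 / 5 = 6 per age arises only if the floor of 30 is taken as the planned count, which the plan never says. This objection stands in full.

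2. *Correlation comes first.* The plan leads with the correlation, which uses all children in a stratum and has reasonable power for r of 0.4 or more. This stands, and it confines the power shortfall to the added ANOVA. It does not supply a comparison between ages.

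3. *The 10/10/10 case is pessimistic.* A stratum should hold at least 50 children, and 10 is a minimum. This stands in part: 20/20/10 raises power from 32% to 45%, still well below 80%. With f = 0.50 or more, the 20/20/10 split would do.

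4. *The age work is worded as exploration.* That is so, and the plan sets no rule that a non-significant age counts as a worsening. Error rates built on such a rule would go beyond the text. But no other listed analysis bears on a primary aim, so the label does not remove the need for a usable estimate.

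A reader might also set the 56 per neurocognitive group (2 x 56 = 112) against 50 per age. That comparison is not clearly among the analyses to be repeated within each age, so the documents do not support a finding on it.

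**Conclusion.** The minimums are arithmetically consistent. The weakness lies in method: each by-age ANOVA may run at one third of the per-category size the plan calls necessary, neither 30 nor 10 is justified, and nothing listed tests whether responsivity changes with age.

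The size depends on assumed values. At alpha 0.05, an effect with 80% power at 30 per category falls to about 32% at 10/10/10 and 45% at 20/20/10. For larger effects the loss is smaller, and the within-age correlation is adequate for r of 0.4 and above. The distribution of anchor answers by age is not given, so how often a stratum would fall near its floor cannot be stated. The missing comparison between ages does not depend on any of these assumptions.

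**What to change.** Estimate the age effect from one model on all children with a cognitive age: change score on anchor, cognitive age and their interaction, for each scale, with age entered continuously or by year. Report the interaction with its confidence interval as the answer on how responsivity varies with age. This extends the anchor-by-level interaction the plan already names for neurocognitive level.

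Present the year-by-year ANOVAs and correlations as descriptive, with counts per anchor category and intervals. State that the floor of 30 per category supports only the pooled ANOVA, and give the basis for 30 and for 10.

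The cost is analysis wording, with no extra patients or data. A continuous age term assumes a form for the trend, so check it against the by-year means. Significance at individual ages would no longer be claimed.
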